APPENDIX 1: ANTICIPATED ADVERSE EVENT DEFINITIONS

Bleeding

An episode of SUSPECTED INTERNAL OR EXTERNAL BLEEDING that results in one or more of the following:

- a. Death,
- b. Reoperation,
- c. Hospitalization,
- d. Transfusion of red blood cells as follows:
 - If transfusion is selected, then apply the following rules:

During first 7 days Post-implant

- ≥ 50 kg: ≥ 4U packed red blood cells (PRBC) within any 24 hour period during first 7 days post-implant.
- <50 kg: ≥20 cc/kg packed red blood cells (PRBC) within any 24 hour period during the first 7 days post-implant

After 7 days Post-implant*

- Any transfusion of packed red blood cells (PRBC) after 7 days following implant with the investigator recording the number of units given. (Record number of units given per 24 hour period).

Note: Hemorrhagic stroke is considered a neurological event and not as a separate bleeding event.

*Any transfusion of ≥ 2U packed red blood cells (PRBC) after 7 days following implant will be considered a serious bleed

Cardiac Arrhythmias

Any documented arrhythmia that results in clinical compromise (e.g., diminished VAD flow, oliguria, pre-syncope or syncope) that requires hospitalization or occurs during a hospital stay. Cardiac arrhythmias are classified as 1 of 2 types:

- 1) Sustained ventricular arrhythmia requiring defibrillation or cardioversion.
- 2) Sustained supraventricular arrhythmia requiring drug treatment or cardioversion.

Pericardial Fluid Collection

Accumulation of fluid or clot in the pericardial space that requires surgical intervention or percutaneous catheter drainage. This event will be subdivided into those with clinical signs of tamponade (e.g. increased central venous pressure and decreased cardiac/VAD output) and those without signs of tamponade.

Device Malfunctions

A Device Malfunction occurs when any component of the MCS system ceased to operate to its designated performance specifications or otherwise fails to perform as intended. Performance specifications include all claims made in the Instructions for Use.

Internal Component Malfunction: Malfunction of any device system component that is implanted within the patient. A malfunction to these components may require further surgery to repair or replace.

External Component Malfunction: Malfunction of a device system component that is used external to the patient and can be replaced or repaired without the need for further surgery.

Device Thrombosis

Device thrombosis is an event in which the pump or its conduits contain a thrombus that results in or could potentially induce circulatory failure. Suspected device thrombus is an event in which clinical or MCS parameters suggest thrombus on the blood contacting components of the pump, cannulae, or grafts. Signs and symptoms should include at least 2 of the 3 following criteria:

- a. Presence of hemolysis
- b. Worsening heart failure or inability to decompress the left ventricle
- c. Abnormal pump parameters

Suspected pump thrombus should be accompanied by 1 or more of the following events or interventions:

- i. Treatment with intravenous anticoagulation (e.g., heparin), intravenous thrombolytics (e.g., tPA), or intravenous antiplatelet therapy (e.g., eptifibatid, tirofiban)
- ii. Pump replacement
- iii. Pump explantation
- iv. Urgent transplantation (UNOS status 1A)
- v. Stroke
- vi. Arterial non-CNS thromboembolism
- vii. Death

Confirmed device thrombus is an event in which thrombus is confirmed by Thoratec returned product analysis to be found within the blood contacting surfaces of device inflow cannula or outflow conduit or grafts. This can also be reported via direct visual inspection or by incontrovertible contrast radiographic evidence or by the absence of an appropriate Doppler flow signal that results in or could potentially induce circulatory failure or result in thromboembolism.

Hemolysis*

A plasma-free hemoglobin value that is greater than 40 mg/dl, concomitant with a rise in serum LDH above three times the upper limit of normal, in association with clinical signs associated with hemolysis (e.g., anemia, low hematocrit, hyperbilirubinemia) occurring after the first 72 hours post-implant.

*Hemolysis in the presence of worsening heart failure or inability to decompress the left ventricle or abnormal pump parameters should be reported as suspected device thrombosis, not as hemolysis

Hepatic Dysfunction

An increase in any two of the following hepatic laboratory values (total bilirubin, aspartate aminotransferase/AST and alanine aminotransferase/ALT) to a level greater than three times the upper limit of normal for the hospital, beyond 14 days post-implant (or if hepatic dysfunction is the primary cause of death).

Hypertension

Blood pressure elevation of a mean arterial pressure greater than 110 mm Hg, despite anti-hypertensive therapy.

Major Infection

A clinical infection accompanied by pain, fever, drainage and/or leukocytosis that is treated by anti-microbial agents (non-prophylactic). A positive culture from the infected site or organ should be present unless strong clinical evidence indicates the need for treatment despite negative cultures. The general categories of infection are listed below:

Localized Non-Device Infection

Infection localized to any organ system or region (e.g. mediastinitis) without evidence of systemic involvement (see sepsis definition), ascertained by standard clinical methods and either associated with evidence of bacterial, viral, fungal or protozoal infection, and/or requiring empirical treatment.

Percutaneous Site and/or Pocket Infection

A positive culture from the skin and/or tissue surrounding the drive line or from the tissue surrounding the external housing of a pump implanted within the body, coupled with the need to treat with antimicrobial therapy, when there is clinical evidence of infection such as pain, fever, drainage, or leukocytosis.

Internal Pump Component, Inflow or Outflow Tract Infection

Infection of blood-contacting surfaces of the LVAD documented by positive site culture.

Sepsis

Evidence of systemic involvement by infection, manifested by positive blood cultures and/or hypotension.

Myocardial Infarction

Two categories of myocardial infarction will be identified:

Peri-Operative Myocardial Infarction

The clinical suspicion of myocardial infarction together with CK-MB or Troponin > 10 times the local hospital upper limits of normal, found within 7 days following VAD implant together with ECG findings consistent with acute myocardial infarction. (This definition uses the higher suggested limit for serum markers due to apical coring at the time of VAD placement, and does not use wall motion changes because the apical sewing ring inherently creates new wall motion abnormalities.)

Non-Perioperative Myocardial Infarction

The presence at > 7 days post-implant of two of the following three criteria:

- a) Chest pain which is characteristic of myocardial ischemia,
- b) ECG with a pattern or changes consistent with a myocardial infarction, and
- c) Troponin or CK (measured by standard clinical pathology/laboratory medicine methods) greater than the normal range for the local hospital with positive MB fraction ($\geq 3\%$ total CK). This should be accompanied by a new regional LV or RV wall motion abnormality on a myocardial imaging study.

Neurologic Dysfunction

Any new, temporary or permanent, focal or global neurological deficit, ascertained by a standard neurological history and examination administered by a neurologist or other qualified physician and documented with appropriate diagnostic tests and consultation note; or an abnormality

identified by surveillance neuroimaging. The examining physician will classify the event as defined below:

- a. Transient ischemic attack*, defined as an acute transient neurological deficit conforming anatomically to arterial distribution cerebral ischemia, which resolves in < 24 hours and is associated with no infarction on brain imaging (head CT performed >24 hours after symptom onset; or MRI)
- b. Ischemic Stroke*: a new acute neurologic deficit of any duration associated with acute infarction on imaging corresponding anatomically to the clinical deficit, or a clinically covert ischemic stroke seen by surveillance imaging, without clinical findings of stroke or at the time of event recognition.
- c. Hemorrhagic Stroke*: a new acute neurologic deficit attributable to intracranial hemorrhage (ICH), or a clinically covert ICH seen by surveillance imaging, without clinical findings of ICH at the time of event recognition.
- d. Encephalopathy: Acute new encephalopathy** due to hypoxic-ischemic injury (HIE), or other causes, manifest as clinically evident signs or symptoms, or subclinical electrographic seizures found by complete neurological diagnostic evaluation to be attributable to acute global or focal hypoxic, or ischemic brain injury not meeting one of ischemic stroke or ICH events as defined above.
- e. Seizure of any kind
- f. Other neurological event (non-CNS event): examples include neuro muscular dysfunction or critical care neuropathy

*Modified Rankin Score will be used to classify the severity of all strokes

**Acute encephalopathy is a sign or symptom of some underlying cerebral disorder, and is manifest as depressed consciousness with or without any associated new global or multifocal neurologic deficits in cranial nerve, motor, sensory, reflexes and cerebellar function.

Psychiatric Episode

Disturbance in thinking, emotion or behavior that causes substantial impairment in functioning or marked subjective distress requiring intervention. Intervention is the addition of new psychiatric medication or hospitalization. Suicide is included in this definition.

Renal Dysfunction

Two categories of renal dysfunction will be identified:

Acute Renal Dysfunction

Abnormal kidney function requiring dialysis (including hemofiltration) in Subjects who did not require this procedure prior to implant, or a rise in serum creatinine of greater than 3 times baseline or greater than 5 mg/dL sustained for over 48 hours.

Chronic Renal Dysfunction

An increase in serum creatinine of 2 mg/dl or greater above baseline, or requirement for hemodialysis sustained for at least 90 days.

Respiratory Failure

Impairment of respiratory function requiring reintubation, tracheostomy or (the inability to discontinue ventilatory support within six days (144 hours) post-VAD implant. This excludes intubation for reoperation or temporary intubation for diagnostic or therapeutic procedures.

Right Heart Failure

Symptoms and signs of persistent right ventricular dysfunction requiring RVAD implantation, or requiring inhaled nitric oxide or inotropic therapy for a duration of more than 1 week at any time after LVAD implantation.

Arterial Non-CNS Thromboembolism

An acute systemic arterial perfusion deficit in any non-cerebrovascular organ system due to thromboembolism confirmed by one or more of the following:

- 1) Standard clinical and laboratory testing
- 2) Operative findings
- 3) Autopsy findings

This definition excludes neurological events.

Venous Thromboembolism Event

Evidence of venous thromboembolic event (e.g. deep vein thrombosis, pulmonary embolism) by standard clinical and laboratory testing.

Wound Dehiscence

Disruption of the exposed surfaces of a surgical incision, excluding infectious etiology, and requiring surgical repair.

Other

An event that causes clinically relevant changes in the Subject's health (e.g. cancer).

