Study Design	
The study will be a prospective, multi-center, unblinded, randomized, controlled, non-inferiority study comparing the HM3 LVAS to the HM II LVAS. The study will be conducted as a staged pivotal study that includes a pre-specified early assessment for safety.
 
Other key elements include:
 
 - Up to 5 centers in the United States (U.S.) will be initiated to enroll up to 10 randomized HM3 Subjects. A pre-specified analysis for safety will be performed after the first 10 randomized HM3 Subjects have completed 30 days of follow-up. The results of this early safety analysis will be reviewed by the Data Safety Monitoring Board (DSMB), after which the DSMB report, along with supporting safety data from the HM3 CE Mark study will be sent to FDA as an IDE supplement, with a request to gain full IDE approval to expand the study to up to a total of 60 centers in the U.S. The first 5 U.S. centers will continue to enroll up to a total of 30 subjects (including those in the early safety analysis) during FDAs review of this IDE Supplement. - An adaptive design will be used, if required to adjust the sample size at a pre-specified time during the study. - Primary Endpoint Analysis 
 - Perform an analysis and submit the Premarket Approval (PMA) when the specified number of Subjects complete 6 months of support for a short term indication - Perform an analysis and submit a PMA supplement when the specified number of Subjects complete 24 months of support for a long term indication - Powered Secondary Endpoint Analysis 
 - Once the Subjects have been enrolled for the primary endpoint analysis, randomization will continue until sufficient Subjects have been enrolled to evaluate a pre-specified powered secondary endpoint. - Analysis of the pre-specified secondary endpoint will be used to update HM3 labeling.
Control Group	The HM II will serve as the control group. Subjects will be randomized 1 HM3 to 1 HM II.

STUDY SYNOPSIS	

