12 EXCLUSION CRITERIA

- 1) Etiology of HF due to or associated with uncorrected thyroid disease, obstructive cardiomyopathy, pericardial disease, amyloidosis, or restrictive cardiomyopathy
- 2) Technical obstacles which pose an inordinately high surgical risk, in the judgment of the investigator
- 3) Existence of ongoing mechanical circulatory support (MCS) other than IABP
- 4) Positive pregnancy test if of childbearing potential
- 5) Presence of mechanical aortic cardiac valve that will not be either converted to a bioprosthesis or oversewn at the time of LVAD implant
- 6) History of any organ transplant
- 7) Platelet count $< 100,000 \times 10^3/L$ ($< 100,000/ml$)
- 8) Psychiatric disease/disorder, irreversible cognitive dysfunction or psychosocial issues that are likely to impair compliance with the study protocol and LVAS management
- 9) History of confirmed, untreated Abdominal Aortic Aneurysm (AAA) > 5 cm in diameter within 6 months of enrollment
- 10) Presence of an active, uncontrolled infection
- 11) Intolerance to anticoagulant or antiplatelet therapies or any other peri/post-operative therapy that the investigator will require based upon the patients' health status
- 12) Presence of any one of the following risk factors for indications of severe end organ dysfunction or failure:
 - a) An INR ≥ 2.0 not due to anticoagulation therapy
 - b) Total bilirubin > 43 $\mu\text{mol/L}$ (2.5 mg/dl), shock liver, or biopsy proven liver cirrhosis
 - c) History of severe chronic obstructive pulmonary disease (COPD) defined by $\text{FEV}_1/\text{FVC} < 0.7$, and $\text{FEV}_1 < 50\%$ predicted
 - d) Fixed pulmonary hypertension with a most recent PVR ≥ 8 Wood units that is unresponsive to pharmacologic intervention
 - e) History of stroke within 90 days prior to enrollment, or a history of cerebrovascular disease with significant ($> 80\%$) uncorrected carotid artery stenosis
 - f) Serum Creatinine ≥ 221 $\mu\text{mol/L}$ (2.5 mg/dl) or the need for chronic renal replacement therapy
 - g) Significant peripheral vascular disease (PVD) accompanied by rest pain or extremity ulceration
- 13) Patient has moderate to severe aortic insufficiency without plans for correction during pump implant
- 14) Pre albumin < 150 mg/L (15mg/dL) or Albumin < 30 g/L (3 g/dL) (if only one available); pre albumin < 150 mg/L (15mg/dL) and Albumin < 30 g/L (3 g/dL) (if both available)
- 15) Planned Bi-VAD support prior to enrollment

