16.2 Baseline Assessments

The following baseline assessments will be performed within 30 days prior to implant (refer to Section 34, Table 2 for the Study Visit Schedule):

1. Medical History, including cardiovascular history with etiology of HF and duration of HF
2. Physical Exam, including height, weight and vital signs
3. Current Medications (total daily dose): anticoagulation/anti platelet, antibiotics, and cardiovascular medications including ACE inhibitors, ARBs, beta blockers, statins, nitrates, allopurinol, aldosterone blockers, and diuretics including metolazone, hydrochlorothiazide and furosemide
4. Laboratory Assessments:
 - a. Hematology: hemoglobin, hematocrit, percent lymphocytes, platelet count, WBC, PHgb, Bleeding/Coagulation: INR, aPTT/PTT, PT
 - b. Chemistry: Potassium, Blood Urea Nitrogen (BUN), creatinine, uric acid, sodium, eGFR (calculated), serum BNP or NT-proBNP, total protein, albumin or pre-albumin, CRP or hs-CRP
 - c. Lipids: cholesterol
 - d. Liver Enzymes: LDH, AST, ALT, total bilirubin
5. Hemodynamic Measurements
6. Echocardiogram: LVEF, LVEDD, LVESD, AV opening, AI, MR, TR including severity and/or grade.
7. Electrocardiogram (ECG): Heart Rate, QRS duration, Arrhythmias
8. 6 Minute Walk Test (6MWT) (if Subject is able; reason must be provided if not performed)

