34 MOMENTUM 3 IDE STUDY VISIT SCHEDULE

Table 2 – Schedule of Events for Randomized Subjects

	Screening ¹	Baseline ¹	Implant	Post-Op Day 1 (+/- 1 day)	1 Week Post Implant (+/- 1 day)	Discharge (-1 day)	30 Days Post Implant (+/- 7 days)	90 Days Post Implant (+/- 30 days)	180 Days Post Implant (+/- 30 days)	360 Days Post Implant (+/- 30 days)	540 Days Post Implant (+/- 30 days)	720 Days Post Implant (+/- 30 days)	As Occurs
Inclusion/ Exclusion	X												
Enrollment / Randomization	X ¹⁷												
Demographics	X												
Intended Use ¹¹	X												
General and Cardiac Medical History		X											
Current Medications / Cardiovascular Medications ⁹		X	X		X	X	X	X	X	X	X	X	
Physical Exam		X											
Vital Signs ²		X			X	X	X	X	X	X	X	X	
Hemodynamic Measurements ³		X											
Laboratory Assessments		X			X	X	X	X	X	X	X	X	
Echocardiogram		X		X ¹⁵	X	X	X	X	X	X	X	X	
ECG		X											
Chest X-ray ¹³ (PA and Lateral)				X ¹⁶			X		X	X		X	
Modified Rankin Score ¹⁹		X	X ⁶		X ⁶	X ⁶	X ⁶	X ⁶	X ⁶	X ⁶	X ⁶	X ⁶	X ⁶
NYHA Classification ⁵		X				X	X	X	X	X	X	X	
INTERMACS Profile ¹⁸		X											
6 Minute Walk Test		X					X	X	X	X	X	X	
EQ-5D-5L		X					X	X	X	X	X	X	
KCCQ		X						X	X	X	X	X	

Thoratec® Corporation
MOMENTUM 3
IDE Clinical Study Protocol

	Screening ¹	Baseline ¹	Implant	Post-Op Day 1 (+/- 1 day)	1 Week Post Implant (+/- 1 day)	Discharge (-1 day)	30 Days Post Implant (+/- 7 days)	90 Days Post Implant (+/- 30 days)	180 Days Post Implant (+/- 30 days)	360 Days Post Implant (+/- 30 days)	540 Days Post Implant (+/- 30 days)	720 Days Post Implant (+/- 30 days)	As Occurs
VO ₂ Max ¹⁰		X											
Implant Data/CPB Time/Blood Products			X										X
HM II and HM3 Pump Parameters ⁷			X		X	X	X	X	X	X	X	X	X ¹⁴
Concurrent Procedures at Pump Implant			X										X
Subject Status					X	X	X	X	X	X	X	X	X
Subject Outcome					X	X	X	X	X	X	X	X	X
ICU Time						X							
Rehospitalizations							X	X	X	X	X	X	X
HM3 Pump Log Files ⁸			X	X	X	X	X	X	X	X	X	X	X ¹⁴
HM II Pump Log Files													X ¹⁴
Adverse Events ⁴			X		X	X	X	X	X	X	X	X	X
Device Malfunctions ⁴			X		X	X	X	X	X	X	X	X	X
Operative Procedures ⁴					X	X	X	X	X	X	X	X	X
Pump Replacements / Explants / Exchanges ⁴					X	X	X	X	X	X	X	X	X
Driveline Management Assessment					X	X	X	X	X	X	X	X	X
Collection of UB-04 Form						X							X ¹²
Autopsy													X

¹ Screening and Baseline assessments can be conducted as one visit or separate visits.

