8.9 Analysis of Adverse Events

All pre-defined adverse events will be captured. Tables will be created for HM III and HM II AEs that show the by-treatment incidences of all adverse events and the by-treatment event rate per patient year of support. Serious adverse events (SAEs) will be analyzed in a similar manner as AEs. Differences in event rates between the treatment arms will be analyzed using Fisher's Exact test or Poisson regression, as appropriate.

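### Covert lesions on surveillance imaging count as strokes but no brain imaging is scheduled, so the recorded stroke incidence depends partly on how often unblinded sites scan each arm

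*Protocol*

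**What the plan says.** **Definition.** Protocol Appendix 1, Neurologic Dysfunction, has two routes to a stroke. One is a new acute deficit. The other is a finding without symptoms. For ischemic stroke the second route reads "or a clinically covert ischemic stroke seen by surveillance imaging, without clinical findings of stroke or at the time of event recognition". For hemorrhagic stroke it reads "or a clinically covert ICH seen by surveillance imaging, without clinical findings of ICH at the time of event recognition". The opening definition of neurologic dysfunction likewise accepts, as an alternative to a new deficit, an abnormality "identified by surveillance neuroimaging". Surveillance imaging is not defined.

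**Schedule.** Protocol 16.2 opens with "The following baseline assessments will be performed within 30 days prior to implant" and lists an echocardiogram and an ECG, but no brain imaging. Sections 16.3 to 16.7 add none. Table 2, "Schedule of Events for Randomized Subjects", has rows for echocardiogram and chest X-ray and no row for head CT or MRI, including under As Occurs.

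**Design and entry.** The Synopsis describes a "prospective, multi-center, unblinded, randomized, controlled, non-inferiority study comparing the HM3 LVAS to the HM II LVAS". On prior stroke, exclusion 12e covers "History of stroke within 90 days prior to enrollment", so a subject may enter with an older lesion.

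**Analysis.** SAP 8.9 (and Protocol 13.10) plans tables that "show the by-treatment incidences of all adverse events and the by-treatment event rate per patient year of support", with arms compared by Fisher's exact test or Poisson regression. Neither section separates covert from overt strokes. Protocol 13.1 and SAP 8 restrict adverse event analysis to events after the implant procedure has begun.

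**The concern.** An event that can be found only by a scan is counted in proportion to scanning. The protocol does not fix scanning, so each site decides whom to image and knows the device when it decides. Randomization balances the true risk of stroke; it does not balance imaging after implant. If one arm is scanned more often, for whatever reason, equal true risk can appear as a device difference in stroke.

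A second, smaller problem is dating. With no scheduled baseline scan, it may be impossible to tell whether a covert lesion first seen after implant arose before or after it. The requirement that a deficit be new and acute belongs to the symptomatic route, not to the covert one.

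At stake is the between-arm reading of stroke as one of the adverse events in the secondary safety endpoint. Protocol sections 1 and 25 name fewer adverse events as a possible benefit of the HM3, so readers will look at this comparison.

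**Working it through.** The plan states no figure for scanning, covert lesions or their effect, so there is nothing to reproduce. The calculation below shows only how large the effect could be.

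**Inputs from the documents**
- Overt stroke rate p = 19% in both arms. This is the 24-month upper limit for stroke in Protocol Table 1, used here as an equal true rate. It matches the 24-month follow-up of the cohorts below.
- 183 per arm (SAP 8.4.3) and 514 per arm (SAP 8.16). These are randomized numbers; the treated numbers may be a little lower.
- Two-sided 0.05 level (Protocol 13.14, SAP 8.13), Fisher's exact test.

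**Assumptions, not in the documents**
- Share of each arm scanned, s: 40% in one arm and 20% in the other.
- Chance that a scan shows a covert lesion, c: 10% or 20%.
- Scanning and lesions are independent of overt stroke.

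**Formula.** Recorded incidence = 1 − (1 − p)(1 − s × c) = p + (1 − p) × s × c.

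**c = 10%**
- 20% scanned: 0.19 + 0.81 × 0.20 × 0.10 = 20.62%
- 40% scanned: 0.19 + 0.81 × 0.40 × 0.10 = 22.24%
- False difference: 1.62 points

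**c = 20%**
- 20% scanned: 0.19 + 0.81 × 0.20 × 0.20 = 22.24%
- 40% scanned: 0.19 + 0.81 × 0.40 × 0.20 = 25.48%
- False difference: 3.24 points

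**Rejection rate of Fisher's test, summed exactly over the two binomial distributions**

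| Scanning | c | 183 per arm | 514 per arm |
|---|---|---|---|
| 40% v 20% | 10% | 5.1% | 8.4% |
| 40% v 20% | 20% | 9.0% | 20.8% |
| 30% v 30% | 10% or 20% | 3.7% to 3.8% | 4.2% |

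**Sensitivity to p.** With p = 12% (Table 1's 6-month limit), 40% v 20% scanning gives 13.76% v 15.52% at c = 10% and 15.52% v 19.04% at c = 20%. The rejection rates at 514 per arm are 10.9% and 29.2%. I do not rest the point on these, because a 6-month rate does not belong with a 24-month cohort.

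**The case against.** **No claim rests on this test.** SAP 7(b) says that no statistical claims will be made on secondary endpoints, and Protocol sections 1 and 25 call the evaluation of reduced adverse events descriptive. This stands and lowers the stakes. The tests are still planned at 0.05, without adjustment for multiplicity, and will be reported.

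**The covert route may seldom apply.** Imaging done to work up thrombosis or bleeding is prompted by an event and is not surveillance in the ordinary sense. With no surveillance scheduled, few lesions may qualify. That is a fair reading. But the term is undefined, sites may read it more widely, and the plan does not say which reading governs.

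**Old lesions are already excluded.** A reader might infer that old lesions can simply count as new. The documents do not support that. Only events after the start of implant are analyzed, medical history and a Rankin score are taken at baseline, and an independent Clinical Events Committee adjudicates (Protocol 31.1.2). A lesion known to be old is out. What remains is that some covert lesions may be hard to date. The committee can help with dating, but it cannot equalize who is scanned.

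**Severity is graded.** The Rankin score classifies all strokes, so mild ones can be identified. But a low score does not separate a covert lesion from an overt stroke that has resolved, and no analysis by severity is pre-specified.

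**Covert lesions are real harm.** Removing them from the main comparison could hide device-related infarcts or hemorrhages. This stands, and it is why the fix adds an analysis and replaces none.

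**Conclusion.** The point holds as a gap in ascertainment for a secondary safety endpoint, and it is minor. The stroke definition relies on imaging that the protocol does not schedule, in a trial where the arm is known, and no planned analysis separates the events that depend on scanning from those that do not.

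Under the assumed scanning imbalance and a 19% overt rate, the false difference is 1.6 to 3.2 points. The false rejection rate is 8% to 21% at 514 per arm and 5% to 9% at 183, against about 4% when scanning is equal. The scan shares and lesion yields are my assumptions. The effect shrinks to nothing as scanning becomes equal.

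Two stronger readings are not supported. The first is that the stroke comparison is biased: the documents show no imbalance in scanning, only exposure to one. The second is that the primary result is at risk: Protocol 13.3 counts only strokes with a Rankin score above 3, which a lesion without clinical findings should rarely reach.

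**What to change.** In Protocol 13.10 and SAP 8.9:

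1. Keep the all-stroke tabulation as Appendix 1 defines it.
2. Tabulate overt strokes (with a clinical deficit) and covert lesions separately by arm.
3. Pre-specify a between-arm comparison of overt strokes only, for incidence and for rate per patient-year, to be read alongside the all-stroke result.
4. State that a lesion found while covert that later becomes symptomatic counts as overt from symptom onset.

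**Cost.** One extra analysis, and fewer events, hence less precision, in the overt-only comparison. A covert/overt flag is needed. The case report form is not among the documents, so if it does not hold that item, the flag must come from the Clinical Events Committee or neurology record. No scan is added and clinical management does not change.
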